3.4 Withdrawal and discontinuation

No tissue samples will be taken from patients withdrawing consent prior to the endoscopy or bariatric surgery. If withdrawal from the study occurs after tissue sampling but prior to sample analysis, clinical data and the sample will be destroyed and work-up of the tissue not performed. Discontinued patients will be replaced in order to reach the pre-specified number of study participants. If withdrawal occurs after work-up of the sample, clinical and tissue data will be retained in the study and used for analysis in a coded manner. After the analysis, the clinical and tissue data will be irreversibly anonymised.

4 STATISTICS AND METHODOLOGY

4.1. Statistical analysis plan

The study will entail samples collected from patients undergoing endoscopy of the gastrointestinal tract or bariatric surgery at the University Hospital Basel who sign an informed consent allowing to use their

tissue for research purposes. Samples sizes were calculated using G*Power, University Düsseldorf. The primary endpoint will be analyzed by Mann-Whitney U test assuming an alpha-error of 0.05 as limit of significance and a power of 0.95. Based on our preclinical mouse data experiments, we calculated an expected effect size of 2.4 (in terms of absolute numbers of intestinal macrophage subpopulation P1), leading to a necessary group size of 6 subjects per group. However, as we expect greater variance with human data compared to mice due to diet/ lifestyle, we suggest including 10 subjects per group as specified below, accounting for a total of study participants of 60:

Colonic tissue samples:

- Obese weight non-smokers (BMI >32kg/m²), n=10
- Obese smokers (BMI >32kg/m², ≥1 pack cigarettes/d), n=10
- Normal weight non-smokers (BMI <27kg/m²), n=10
- Normal weight smokers (BMI <27kg/m², ≥1 pack cigarettes/d), n=10

Tissue samples of the upper gastrointestinal tract and assessment of nutritional intervention:

- Obese non-smokers (BMI >35kg/m²) undergoing bariatric surgery, n=10
 - o a) Pre-diet: gastric and duodenal biopsies from the preoperative screening gastroscopy
 - o b) Post-diet: jejunal tissue specimen from bariatric surgery
- Normal weight non-smokers (BMI <27kg/m²), n=10

Descriptive statistics will be used for outcome measures. To compare groups (e.g. obese versus lean, smokers versus non-smokers) two-tailed non-parametric tests will be used (Mann-Whitney). A p-value <0.05 will be considered as statistically significant. These statistical analyses will be done with the help of GraphPadPrism.

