2.2 Primary and secondary endpoints

Primary endpoints: In our preclinical studies, we found that mice fed a high fat diet had a shift of intestinal macrophages towards inflammatory subpopulations, which precedes adipose tissue inflammation. We think that intestinal macrophages could also be involved in human metabolic disease. Therefore, our primary endpoint is to investigate:

- 1) the frequency & subpopulations of intestinal macrophages from the *colon* in obese versus lean subjects and smokers versus non-smokers,
- 2) the frequency & subpopulations of intestinal macrophages from the *upper gastrointestinal tract* in obese versus lean subjects,
- 3) the frequency & subpopulations of intestinal macrophages from the upper gastrointestinal tract in obese subjects *before and after a nutritional intervention*.

Secondary endpoint: Besides macrophages, also other intestinal immune cells could be implicated in metabolic disease. For example, one preclinical study found that adaptive immunity might be involved²². In case we do not find clear differences in frequency or subpopulations of intestinal macrophages, we will assess other intestinal immune cells (e.g. B-, T-lymphocytes), and enteroendocrine cells (e.g. L-cells) as a secondary endpoint in an explorative manner. Additionally, we aim to correlate our findings from the biopsy samples with inflammation markers and immune cells in the blood, with microbiota and immune cells in the stool and with the eating habits of the patients.

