3 PROJECT POPULATION AND STUDY PROCEDURES

3.1 Project population, inclusion and exclusion criteria

Study population: To elucidate the role of intestinal immune cells in metabolic disease, human gut samples are necessary, which can be obtained from gut biopsies or surgical samples. As patients will undergo diagnostic endoscopy of the gastrointestinal tract or bariatric surgery for clinical reasons and the standard of care will not be changed by the study, there will be no additional interventions to patients by their participation in the study. Participants fulfilling the following inclusion criteria are eligible for the study:

For *colonic tissue samples*, 10 subjects per group referred to the Department of Gastroenterology at the University Hospital Basel or the doctor's office MagenDarm Basel, for a diagnostic colonoscopy on the basis of symptoms suggestive for irritable bowel syndrome or for a screening colonoscopy for colorectal cancer will be included:

- Obese weight non-smokers (BMI >32kg/m²), n=10
- Obese smokers (BMI >32kg/m², ≥1 pack cigarettes/d), n=10
- Normal weight non-smokers (BMI <27kg/m²), n=10
- Normal weight smokers (BMI <27kg/m², ≥1 pack cigarettes/d), n=10

For *tissue samples of the upper gastrointestinal tract and assessment of nutritional intervention*, 10 subjects per group referred to the Department of Visceral Surgery at the University Hospital Basel, the doctor's office MagenDarm Basel or the Department of Visceral Surgery, Hospital Lindenhof Bern, for bariatric surgery will be included. All bariatric patients receive a screening gastroscopy as standard of care prior to the surgery. Subjects willing to participate will contribute gastric and duodenal biopsies from the preoperative screening gastroscopy as well as an approximately 1cm long piece of the jejunum, which is usually disposed during bariatric surgery. As controls, 10 subjects referred to the Department of Gastroenterology at the University Hospital Basel or the doctor's office MagenDarm Basel, for an upper endoscopy on the basis of dyspeptic symptoms will be included as well.

- Obese non-smokers (BMI >35kg/m²) undergoing bariatric surgery, n=10
 - o a) Pre-diet: gastric and duodenal biopsies from the preoperative screening gastroscopy
 - o b) Post-diet: jejunal tissue specimen from bariatric surgery
- Normal weight non-smokers (BMI <27kg/m²), n=10

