3.3 Study procedures

Screening and inclusion: The study procedure is summarized below. The first patient is planned for September 2018 with a study duration of 2 years. Patients planned for endoscopies of the gastrointestinal tract or bariatric surgeries at the University Hospital Basel, the doctor's office MagenDarm Basel or the Hospital Lindenholz Bern will be screened for inclusion and exclusion criteria and informed about the study by the participating gastroenterologist, endocrinologist or visceral surgeon. Informed consent will be obtained at the latest on the day of the endoscopy or hospital admission for bariatric surgery.

Tissue sampling: Endoscopies or bariatric surgeries will be carried out as per clinical standard of care. Our collaborators are PD Dr. [name] at the Department of Gastroenterology and PD Dr. [name] at the Department of Visceral Surgery, University Hospital Basel, Dr. [name] and [name]. [name] at the doctor's office MagenDarm Basel and PD Dr. [name] at the Department of Visceral Surgery, Hospital Lindenholz Bern. The samples obtained from endoscopies comprise 10 to 12 biopsies per subject including two biopsies being frozen and later on analyzed for inflammatory markers (e.g. TNF α , IL6). The biopsies will be either collected in the Colon transversum in case of colonoscopy or in the stomach and duodenum in case of gastroscopy as we have seen in our mice study different subpopulations depending on the location. The tissue samples from the bariatric surgery are a 1cm piece of the jejunum that would normally be disposed. Additionally, four EDTA and one serum blood tube for the analysis of inflammatory cells and markers in the blood will be taken as well as a single stool sample.

Data: Medical data will be obtained from the patient's electronic health record. The work-up of the tissue specimen, the stool sample and the EDTA blood samples by flow cytometry will be carried out in the laboratory of PD Dr. [name]. Leftover tissue specimen will be snap frozen as well as the serum blood sample after centrifugation. We do not expect biases in our study.

Substudy (validation of diet questionnaire): For validation purposes, normal- and overweight people from the Department of Endocrinology will be asked to fill out a diet questionnaire called „Healthy Eating Index“ (modified after J. Russell) taking about 15 minutes.

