4.2. Handling of missing data

Missing data will not be imputed.

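### The before/after-diet comparison in item 3 of the primary endpoint is paired, but the only test named, Mann-Whitney, is for independent samples

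*Combined protocol and SAP*

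**What the plan says.** Section 2.2 lists three items under the primary endpoint. The third concerns upper gastrointestinal macrophages in obese subjects "before and after a nutritional intervention".

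Section 3.1 says that each bariatric participant "will contribute gastric and duodenal biopsies from the preoperative screening gastroscopy as well as an approximately 1cm long piece of the jejunum". Section 4.1 lists the pre-diet biopsies and the post-diet jejunal specimen as (a) and (b) under one group of n=10.

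On the test, section 4.1 says: "The primary endpoint will be analyzed by Mann-Whitney U test assuming an alpha-error of 0.05 as limit of significance". Further down it adds: "To compare groups (e.g. obese versus lean, smokers versus non-smokers) two-tailed non-parametric tests will be used (Mann-Whitney"). Neither sentence gives item 3 a different method. The protocol contains no paired test, no within-patient correlation and no sample size calculation for a paired comparison. Section 4.2 adds: "Missing data will not be imputed".

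**The concern.** Mann-Whitney takes its null distribution from two independent samples. When one patient supplies both values, the variance of the before/after contrast depends on the within-patient correlation, which the test ignores. Positive correlation makes the test too strict, so a real change of moderate size can be missed. Negative correlation makes it too lenient.

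Item 3 is the only comparison that can answer whether nutritional intervention shifts the macrophages, which is part of the primary objective in section 2.1. If the method is left open, the choice of test, and of stomach or duodenum as the baseline tissue, could be made after the data are seen.

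**Working it through.** **1. Are the data paired?** The colon arm has 4 × 10 = 40 subjects and the upper gastrointestinal arm 2 × 10 = 20. Together they make the 60 stated in section 4.1. The bariatric patients are therefore counted once and give both samples, so item 3 is planned as 10 pairs.

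**2. The plan's own figure.** Inputs from section 4.1: effect size d = 2.4, alpha 0.05, two-tailed, power 0.95. Take noncentral-t power for two independent groups with the Mann-Whitney efficiency factor 3/π, so that the effective group size is N = n × 3/π, the noncentrality is d√(N/2) and df = 2N − 2.

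- n = 6: N = 5.73, noncentrality 2.4 × √2.865 = 4.06, power 0.952.
- n = 5: power 0.894.

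The stated 6 per group is reproduced. It is a calculation for independent groups only.

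**3. Why correlation matters.** With SD σ in each sample and within-patient correlation ρ, the variance of the mean difference over n pairs is 2σ²(1 − ρ)/n. An unpaired test behaves as if it were 2σ²/n. At ρ = 0.5 the true variance is half of that.

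**4. Size of the effect.** The setting is 10 pairs, bivariate normal data with equal SDs, 100,000 simulations per cell and exact two-sided critical values. Mann-Whitney rejects at U ≤ 23 or the mirror value (nominal size 0.0433). Signed-rank rejects at W ≤ 8 or the mirror value (nominal size 0.0488). The documents give neither ρ nor an effect size for item 3, so both are assumptions shown over a range. Each cell gives Mann-Whitney / signed-rank.

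| ρ | Type I error, % | Power at 1.0 SD, % | Power at 1.8 SD, % | Power at 2.4 SD, % |
|---|---|---|---|---|
| −0.3 | 7 / 5 | 51 / 40 | – | 99.5 / 98.1 |
| 0 | 4.3 / 4.9 | 51 / 50 | 95.0 / 93.5 | 99.8 / 99.6 |
| 0.3 | 2 / 5 | 52 / 64 | 97.1 / 98.5 | over 99.9 for both |
| 0.5 | 0.9 / 4.9 | 53 / 79 | 98.3 / 99.8 | over 99.9 for both |
| 0.7 | 0.2 / 4.9 | 55 / 94 | 99.2 / 100 | 100 / 100 |

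At ρ = −0.5 the Mann-Whitney type I error is about 9%. The 1.8 SD column is the effect at which 10 versus 10 independent subjects reach the plan's 95% power.

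**5. Incomplete pairs.** With 8 pairs, 1.0 SD and ρ = 0.5, signed-rank power is 61% and Mann-Whitney power 43%. With 5 pairs the smallest two-sided signed-rank p-value is 2 × (1/2)⁵ = 0.0625, so p < 0.05 cannot be reached.

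**6. Gut site.** The pre-diet tissue is stomach and duodenum. The post-diet tissue is: "Post-diet: jejunal tissue specimen from bariatric surgery". Section 3.3 gives the reason to worry: "we have seen in our mice study different subpopulations depending on the location". With no diet effect but a pure site shift of 1.0 SD and ρ = 0.5, Mann-Whitney rejects in 53% of trials and signed-rank in 78%.

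**The case against.** - **The Mann-Whitney sentence may not be meant for item 3.** It sits within the sample size text, and the later sentence on comparing groups gives only between-group examples. On that reading item 3 simply has no stated method. This is a fair alternative, but a primary comparison without a method still needs correcting.
- **The large power differences need a moderate effect and a sizeable correlation.** This stands. At 2.4 SD almost nothing is lost for ρ ≥ 0, and at 1.8 SD the tests are within 1.5 points of each other for ρ from 0 to 0.7. Different gut sites may keep ρ low: at 1.0 SD the comparison is 51 versus 54% at ρ = 0.1. Nothing in the documents points to negative correlation. Against this, the 2.4 comes from mice, section 4.1 itself expects more variance in humans, and no effect size is given for a diet change.
- **Gut-site confounding is the larger problem.** It is a real limitation, and neither test isolates diet. Because a paired test detects a pure site shift more readily, the test should not be changed without the site caveat.
- **Signed-rank is not exact in all conditions.** It needs symmetric differences under the null. With assumed lognormal data, equal medians and unequal spread, it rejected in about 5.6 to 7.7% of trials. This is a modest excess, but it qualifies the near-5% figures above.
- **Lost pairs may be few.** Section 3.4 replaces discontinued patients. That limits the 8-pair scenario but does not guarantee a usable sample at both time points in every patient.

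**Conclusion.** The concern holds. Item 3 is a within-patient comparison, and the plan as written assigns it an independent-samples test. If Mann-Whitney is applied and the within-patient correlation is not near zero, the p-value does not have its nominal error rate. With 10 pairs the rate falls from 4.3% at ρ = 0 to 0.9% at ρ = 0.5, and at 1.0 SD and ρ = 0.5 the test gives up about 26 points of power (53 versus 79%). The stated group size of 6, and the 10 chosen, are not called into question by this point.

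The figures rest on assumed correlations and effect sizes, normal data and equal SDs. That the test does not match the design rests on none of these. The point should be fixed before analysis; it is confined to one of the three primary items.

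**What to change.** Add to section 4.1, in words such as:

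> Item 3 (before versus after diet) is analysed with the two-sided Wilcoxon matched-pairs signed-rank test on within-patient differences (jejunum post-diet minus duodenum pre-diet) in patients with both samples. The Hodges-Lehmann median difference with 95% CI and the number of pairs are reported. The jejunum minus stomach difference is reported separately as supportive. Mann-Whitney is used only for independent groups. Pre-diet tissue is gastric or duodenal and post-diet tissue is jejunal, so this difference combines diet and gut-site effects.

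Duodenum is only an example; the sponsor should choose the pre-diet tissue and fix it before analysis. The essential parts are the paired test, the named tissue and the site caveat. The interval and the supportive contrast are desirable additions.

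The cost is a few sentences and no extra samples. Patients with only one sample drop out of item 3. Power is 1 to 2 points lower if ρ is 0 (at 1.0 to 1.8 SD). It is also lower if ρ is negative (40 versus 51% at ρ = −0.3 and 1.0 SD), where Mann-Whitney's apparent advantage comes with a type I error of about 7%.

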4.2. Handling of missing data

Missing data will not be imputed.

5 REGULATORY ASPECTS AND SAFETY

5.1 Local regulations / Declaration of Helsinki

This research project will be conducted in accordance with the protocol, the Declaration of Helsinki³, the principles of Good Clinical Practice, the Human Research Act (HRA) and the Human Research Ordinance (HRO)¹ as well as other locally relevant regulations. The Project Leader acknowledges his responsibilities as both the Project Leader and the Sponsor.

5.2 Notification of safety and protective measures (HRO Art. 20)

The project leader is promptly notified (within 24 hours) if immediate safety and protective measures have to be taken during the conduct of the research project. The Ethics Committee will be notified via BASEC of these measures and of the circumstances necessitating them within 7 days.

5.3 Serious events (HRO Art. 21)

If a serious event occurs, the research project will be interrupted and the Ethics Committee notified on the circumstances via BASEC within 7 days according to HRO Art. 21¹.

5.4 Amendments

Substantial changes to the project set-up, the protocol and relevant project documents will be submitted to the Ethics Committee for approval according to HRO Art. 18 before implementation. Exceptions are measures that have to be taken immediately in order to protect the participants.

¹ A serious event is defined as any adverse event where it cannot be excluded, that the event is attributable to the sampling of biological material or the collection of health-related personal data, and which:

- a. requires inpatient treatment not envisaged in the protocol or extends a current hospital stay;
- b. results in permanent or significant incapacity or disability; or
- c. is life-threatening or results in death.

5.5 End of project

Upon project termination, the Ethics Committee is notified within 90 days. Coded medical records and biological material will be retained for 10 years at the Department of Endocrinology, Diabetes and Metabolism or the Department of Biomedicine, University Basel, and then destroyed.

5.6 Insurance

In the event of project-related damage or injuries, the liability of the University Hospital Basel provides compensation, except for claims that arise from misconduct or gross negligence.

6 FURTHER ASPECTS

6.1 Overall ethical considerations

We assume that study results will be generalizable to the general population. As study procedures are performed as per clinical standard of care and no additional procedures are planned just for study purposes, burden and time for participants are well justifiable. Project-specific ethical aspects such as incidental findings seem unlikely as our readouts focus on characterization of intestinal macrophages. Therefore, a fair balance for the study participants seems to be granted.

6.2 Risk-Benefit Assessment

As study participants will undergo endoscopies of the gastrointestinal tract and bariatric surgeries per clinical standard care and the study does not involve additional procedures except a simple blood withdrawal and a stool sample, subjects are not exposed to an additional risk.

The study participant has no immediate benefit from the study. However, elucidation of the role of intestinal macrophages in metabolic disease could help to better understand the pathophysiology of this highly prevalent condition with potential development of targeted therapies in the future.

7 QUALITY CONTROL AND DATA PROTECTION

7.1 Quality measures

For quality assurance, we will develop standard operating procedures for handling and analyses of tissues samples.

7.2 Data recording and source data

Available medical data about date of birth, gender, race, weight, height, BMI, waist and hip circumference, blood pressure, heart rate, smoking status, alcohol consumption, diabetes (including date of diagnosis), other relevant diagnoses, diet and drugs within past month before samples collection, family history regarding diabetes, obesity, cardiovascular diseases, laboratory values for Hb, HbA1c, leucocytes and their differentiation, lipids, CRP, creatinine, AST, ALT, AP and total bilirubin will be collected from hospital records and documented in a coded manner in paper Case Report Forms (CRF). Numerical values will be later transferred into GraphPad prism for statistical analysis. The original source data file will be archived. Changes of the data will be saved as separate files with accompanying information why values had to be modified. Upon the participant's permission, medical information may be given to his or her personal physician or other appropriate medical personnel responsible for her or his welfare.

Data retrieved from biological material regarding intestinal macrophages will be stored in a coded manner in GraphPad prism files upon analysis.

Participants will be asked whether the data obtained during this research project may be used for subsequent projects or secondary analyses.

7.3 Confidentiality and coding

Medical data obtained for this study is confidential and is only accessible to authorized personnel who require the data to fulfil their duties within the scope of the research project. Disclosure to third parties

other than those noted below is prohibited. Confidentiality of the subjects will be maintained by assigning subjects an ID number, keeping identifiers separate from the data and storing data in a locked file in the department of Endocrinology, Diabetes and Metabolism. The principle investigator and the co-investigators will have access to the encryption list.

Biological material in this project is not identified by participant name, but by a unique ID number. Biological material is appropriately stored in a restricted area only accessible to authorized personnel.

7.4 Retention and destruction of study data and biological material

Records and documents pertaining the conduct of this study, including CRFs, consent forms, laboratory test results and clinical notes will be retained for 10 years at the Department of Endocrinology, Diabetes and Metabolism, University Hospitals Basel, and then destroyed. Remaining tissue samples will be archived and used for additional analyses if deemed appropriate. The Department of Endocrinology complies with regulations of its own biobank.

8 FUNDING / PUBLICATION / DECLARATION OF INTEREST

PD [name] has obtained funding from the Velux-Foundation and from the Swiss National Science Foundation. There is no conflict of interest between the funding bodies and the researchers.

